1. SYNOPSIS

Study Title	Pilot Study for a randomised trial comparing the influence of forced air versus resistive fabric warming technologies on post-operative infection rates following orthopaedic implant surgery in adults.	
Short title	Reducing Implant Infection in Orthopaedics (RIIiO) Pilot Study	
Acronym	RIIiO Pilot Study	
Trial Design	Parallel group, open label 1:1 randomised pilot study comparing post- operative infection rates following orthopaedic implant surgery using direct contact Resistive Fabric Warming (RFW) or Forced Air Warming (FAW)	
Trial Participants	Adults of 60 years or over undergoing hemiarthroplasty following hip fracture	
Planned Sample Size	There is no upper limit for the sample size. Progression rules for the definitive trial will include a projection of 100 participants per year at each pilot site. Participants will be recruited over a minimum period of 12 months at each site.	
Follow-Up Duration	90 days from the date of surgery	
Planned Trial Period	14 th November 2016 to 31 st December 2018	
Primary Objective	The primary objective of the pilot study is to inform data management and recruitment strategies for a definitive trial comparing infection rates following orthopaedic surgery with two warming technologies. The primary objective of the full trial: "Is there a significant difference in the incidence of post-operative infection after hemiarthroplasty using Forced Air Warming (FAW) as compared to Resistive Fabric Warming (RFW)?"	
Secondary Objectives	The secondary objective of the pilot study is to explore the feasibility of collecting resource use and quality of life data, to inform the design of the health economics component of the proposed fully powered trial.	
	The secondary objective of the full trial: "Is there a significant cost- effectiveness advantage to the NHS of using either direct contact resistive fabric warming (RFW) or forced air warming (FAW)?"	
Primary Endpoints	Numbers recruited and observed event rate for definitive deep surgical site infection (SSI) within 90 days of surgery.	
Secondary Endpoints	Superficial SSI, inadvertent perioperative hypothermia (IPH), length of hospital stay, patient reported outcome measures for quality of life score (EQ-5D-5L), resource utilisation and serious adverse events (SAEs) including death.	
Investigational Medicinal Products		
	None	

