7.3. Informed Consent

Patients with a hip fracture are a clinical priority for urgent operative care and will usually undergo surgery on the next available operating list. Such patients have a high incidence of comorbidities, will inevitably have suffered trauma and are likely to either be in pain or to have received opiate analgesia. It is therefore understandable that patients find their initial treatment in hospital frightening, confusing or disorientating. In this situation, the focus necessarily lies on obtaining consent for surgery (where possible) and on informing the patient and next of kin about the immediate clinical care plan. It is often either inappropriate or not possible to ask potential participants to review trial documentation, weigh up the information and communicate an informed decision as to whether they would wish to participate.

Conducting research in an emergency setting is regulated by the Mental Capacity Act 2005. Given the number of factors influencing capacity or the ability to communicate an opinion, we will act in accordance with section 32, subsection 9b of the Mental Capacity Act. Those patients who are listed for surgery on the next available operating list will not be approached for consent prior to their surgery but we will approach an appropriate consultee. They will be provided with the study information and be given the opportunity to ask questions and discuss the study, after which their verbal agreement will be recorded. Where possible and appropriate, a personal consultee will be approached. Where necessary, a nominated consultee will be identified to advise the research team. The nominated consultee will be a clinician responsible for the

patient during their admission unless they are also a member of the research team, in which case an independent clinician will be asked to provide an opinion.

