7.5. Baseline and Perioperative Assessments

Data for baseline assessments will be captured from routine clinical care records. The local study team will record the following in the CRF:

- 1) Age
- 2) Gender
- 3) Weight/Height (to derive Body mass index)
- 4) American Society of Anaesthesiologists (ASA) physical status classification
- 5) Anatomical side affected
- 6) Date of admission
- 7) Date of surgery
- 8) Randomisation arm (FAW or RFW)
- 9) Adherence to randomised strategy
- 10) Duration of surgery
- 11) Use of UCV in theatre
- 12) Surgical procedure
- 13) Antimicrobial prophylaxis
- 14) Immuno-suppressants
- 15) Co-Morbidities
- 16) Continuous temperature monitoring (3M SpotOn Zero Flux Thermometry)
- 17) Baseline EQ-5D-5L measures

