7.7. Definition of End of Study

The end of the study is defined as the date of the last follow-up telephone call to the last participant recruited. Any planned formal analyses of the data will take place after this time point.

8. WARMING METHOD and TEMPERATURE MONITORING

The participants recruited to this study will all undergo hemiarthroplasty. During their surgery the patient will be kept warm as part of their standard care. The primary method used will be either Forced Air Warming (FAW) or direct contact Resistive Fabric Warming (RFW) depending on the randomisation arm to which they have been allocated. Both FAW and RFW are established and licensed for use in the UK and are equally effective at preventing inadvertent perioperative hypothermia (Negishi et al.2003). The warming devices will be used in accordance with national guidelines as defined in NICE CG65. Where necessary for optimal clinical care, additional warming methods can be employed at the discretion of the supervising clinician. Standard clinical care would normally include actively warming intravenous fluids and blood products in all patients.

Temperature will be monitored throughout the surgical procedure at all recruiting sites. All thermometers will be calibrated according to the standard protocol at each site. Where possible, site will use the 'SpotOn zfd' temperature monitoring system provided by the company 3MTM (Patient Warming Solutions).

As part of standard clinical care the patient's temperature will be measured and documented before induction of anaesthesia and every 30 minutes until the end of surgery. For the binary analysis, IPH will be defined as a temperature of <36°C at the end of surgery.

In addition, we will use the SpotOn zfd to log a continuous readout to provide the following data:

- a) IPH at any time during surgery and at the end of surgery/arrival in the recovery room
- b) Area under the curve for total hypothermia time during surgery
- c) Weighted hypothermia time (i.e. time spent at 35.5°C is more significant than time spent at 35.9°C)

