10.3. Analysis of Outcome Measures for the full trial

Pending recommendations arising from the pilot study, we assume that the analysis of outcome measures for the full trial will take the following form:

Analysis of the primary endpoint:

Based on the ITT population (i.e. participants analysed according to their allocated trial arm, regardless of their compliance with the protocol), the proportions of participants in either treatment arm experiencing a definitive deep surgical site infection within 90 days from surgery will be calculated.

We will determine the superiority of either of the two trial interventions by assessing if there is a statistically significant difference in the log-odds of infection between the randomised treatment arms using a logistic regression model with randomised treatment as a fixed effect; superiority of either intervention is defined by the treatment coefficient being statistically significant at the 5% level. Covariates considered *a priori* to be prognostic of outcome may be included to give an adjusted odds ratio. These would be agreed by consensus and written into the full statistical analysis plan and signed off prior to analysis of unblinded data.

Secondary analyses will include a per protocol analysis based on all participants who have received their randomised intervention. A survival analysis will be performed to assess potential differences in the time to diagnosis of definitive deep surgical site infections. Health economic evaluation will be conducted by a dedicated health economist based on capital, maintenance and treatment costs, as well as EQ-5D-5L data, and will include the costs of complications.

Other secondary endpoint analyses will include regression models to calculate estimates of treatment differences for the primary and secondary outcomes unadjusted (primary analysis) and adjusted for age and co-morbidities (secondary analyses). These secondary analyses will focus on the consistency of point estimates and 95% confidence intervals rather than formal statistical significance testing.

Pre-defined subgroup analyses will use interaction tests to explore the consistency of treatment effects by trial site.

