11. ECONOMIC EVALUATION

Good practice recommendations for cost-effectiveness analyses (Ramsey et al, 2015) suggest concentrating on the measurement of large cost drivers, with less focus on resources that are not expected to differ between different treatments. Estimation of cost-effectiveness is therefore an iterative process and, by including a health economic component, it is possible to consider how the methods might be refined in any future more definitive study.

Methods

In order to estimate costs, we will measure theatre time, length of stay and hospital re-admissions. Unit costs (e.g. Curtis et al, 2015, Dept of Health, 2014-2015) will subsequently be assigned to items of resource use. However, in order to estimate the unit costs associated with both the RAW and FAW intervention, each site will be asked to complete a short questionnaire which would request information such as the purchase price of intervention specific equipment and whether items are disposed of after each patient or re-used.

For benefits, the EQ-5D-5L (Herdman et al, 2011) will be used to measure quality of life, enabling QALY (Quality Adjusted Life Year) scores to be calculated. This will be requested at baseline, day 30 and day 90. The self-complete version of the EQ-5D-5L will be used for those who give consent, consultees will be asked to complete the proxy version of the EQ-5D-5L.

Analysis

The main purpose of the analysis is to inform the decision regarding how and what cost and effect data would be collected within the proposed fully powered trial. Thus, we will estimate completion rates and seek to identify big cost drivers, in order to inform this decision.

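### The adjusted models leave out pre-induction temperature and baseline EQ-5D-5L, and the EQ-5D-5L baseline has no defined timing

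*Protocol*

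**What the plan says.** **Models.** Section 10.3 opens as an outline: "Pending recommendations arising from the pilot study, we assume that the analysis of outcome measures for the full trial will take the following form". For the primary endpoint it leaves room for further covariates: "Covariates considered *a priori* to be prognostic of outcome may be included to give an adjusted odds ratio", to be settled in the full statistical analysis plan. The later paragraph on regression models for the primary and secondary outcomes names its own set, "unadjusted (primary analysis) and adjusted for age and co-morbidities (secondary analyses", and does not repeat that deferral. The synopsis lists the secondary endpoints as "Superficial SSI, inadvertent perioperative hypothermia (IPH), length of hospital stay, patient reported outcome measures for quality of life score (EQ-5D-5L), resource utilisation". Safety events complete that list.

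**Temperature.** Section 8 has temperature "measured and documented before induction of anaesthesia and every 30 minutes until the end of surgery" as part of standard care. Binary hypothermia (IPH) is a reading below 36°C at the end of surgery. The data list in section 7.5 includes continuous temperature monitoring but has no separate item for the pre-induction reading.

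**EQ-5D-5L.** Section 7.5 includes a baseline EQ-5D-5L under the statement "Data for baseline assessments will be captured from routine clinical care records". Section 11 says instead that the questionnaire is requested at baseline, day 30 and day 90: "The self-complete version of the EQ-5D-5L will be used for those who give consent", and consultees fill in the proxy version. Under section 7.3, patients listed for the next available operating list, which is the usual case, "will not be approached for consent prior to their surgery but we will approach an appropriate consultee". The participant is first approached after recovering from surgery, and consent before surgery is described as occasional. Section 7.4 places randomisation before surgery. The script in Appendix B asks about health TODAY.

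**The concern.** There are two linked problems.

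First, an outcome's own starting value is often its strongest predictor. A patient who is already cold before the device is applied is more likely to be cold at the end, whatever the allocation. Leaving that reading out, when it is already documented, discards precision on the outcome closest to the intervention. The same holds for EQ-5D-5L at days 30 and 90.

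Second, the EQ-5D-5L baseline may not be a baseline. A self-completed score about today's health, taken after recovery from the operation, reflects the fracture, the surgery and the days elapsed since, and it follows the allocated warming. It could not safely be used as a pre-randomisation covariate, and QALY calculations would start from it. This concerns data collection, so a later analysis plan cannot repair it. It also matters now: section 4 makes confirming the health-economic methodology the pilot's secondary objective, and section 3 carries pilot data into the final analysis.

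**Working it through.** **1. The plan's own figure.** Section 3 gives 2.5% deep infection, a 1% absolute reduction, 90% power, 5% significance and about 8630 participants. Sidedness is not stated; two-sided is assumed.

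- Uncorrected: n = [1.960·√(2·0.02·0.98) + 1.282·√(0.025·0.975 + 0.015·0.985)]² / 0.01² = 4117 per arm.
- With continuity correction: n/4·[1 + √(1 + 4/(n·0.01))]² = 4315 per arm, or 8630 in total.

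This matches exactly. It concerns the primary endpoint and does not depend on the covariates discussed here.

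**2. Which outcomes have an own baseline.** IPH/temperature (pre-induction reading) and EQ-5D-5L do. Superficial infection, length of stay, resource use and serious adverse events do not.

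**3. Precision for a continuous outcome.** With correlation r between baseline and outcome, adjustment multiplies the residual variance by 1 − r² and the interval width by √(1 − r²). The protocol gives no r, so it is assumed. It should be read as the correlation left after age and co-morbidities.

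| r | 1 − r² | √(1 − r²) | Interval narrower by |
|---|---|---|---|
| 0.3 | 0.91 | 0.954 | 5% |
| 0.4 | 0.84 | 0.917 | 8% |
| 0.5 | 0.75 | 0.866 | 13% |
| 0.6 | 0.64 | 0.800 | 20% |

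These ratios do not depend on sample size.

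**4. Binary IPH.** Simulation with 300 participants, an assumed 0.3 SD shift and a cut-off at −0.3 SD gave these powers for a logistic model without and then with the baseline:

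- r = 0.3: 54% to 56% (800 replicates) and 49% to 52% (1,500 replicates).
- r = 0.5: 53% to 61% and 50% to 57%.

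The gain is 2 to 3 points at r = 0.3 and 7 to 8 points at r = 0.5. For continuous temperature at the same size, power is Φ(0.3·√300/(2·√(1 − r²)) − 1.96). That is 74% unadjusted, 78% at r = 0.3 and 85% at r = 0.5. An adjusted odds ratio is conditional on starting temperature, so its interval should not be compared width for width with the unadjusted one.

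**5. Weight of the baseline in a 90-day QALY.** By the trapezoid rule over days 0, 30 and 90, the scores carry 15, 45 and 30 days. The baseline weight is 15/365.25 = 0.041. An assumed chance imbalance of 0.02 to 0.05 in baseline utility moves the QALY difference by 0.041 × 0.02 = 0.0008 to 0.041 × 0.05 = 0.0021.

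**6. Order of events on the usual route.** Consultee's verbal agreement (7.3), randomisation before surgery (7.4), surgery with the allocated device (8), first approach to the participant after recovery (7.3), self-completion by those who consent (11). A self-completed baseline therefore falls after randomisation and surgery. A proxy score could be taken at the first step, but no section asks for it then. The day 30 and day 90 contacts have windows (7.6); the baseline has none.

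**The case against.** Section 10.3 is an explicit outline. The pilot itself only summarises outcomes by arm (10.1), and covariate choice is normally settled in an analysis plan, which is not available here. An unadjusted analysis with an adjusted one in support is valid. All of this stands, and it makes the covariate point modest. It does not remove it, because the sentence on the regression models names a specific adjustment set and the deferral to the analysis plan is written for the primary-endpoint model.

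The power gains at 300 participants do not carry over to a trial of 8630. There the unadjusted z for a 0.3 SD effect is 0.3·√8630/2 = 13.9, so power is near 100% either way. Section 10.3 also puts estimates and intervals ahead of significance testing for these analyses. That stands too, so interval width is the right measure. The larger gains apply to continuous measures; section 8 lists area under the curve and weighted hypothermia time, but not end-of-surgery temperature as such.

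A reader might infer that most EQ-5D-5L baselines will be post-operative. The protocol gives no share. Consultees are approached before surgery, section 14.7 expects consultee agreement for a significant number of participants, and they complete the proxy form, so pre-operative scores are possible. Section 5 also allows telephone contact at baseline, which softens the reference to routine records but does not say when the score is taken.

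A recalled pre-fracture score is not an obvious remedy. It would still be collected after allocation in an open-label trial, and as a QALY starting point it would describe health before the injury. The fix therefore limits its use.

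**Conclusion.** The point holds in two limited parts.

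- **Covariates.** For IPH/temperature and EQ-5D-5L only, the named adjustment set omits the outcome's own baseline. The cost is precision: adjustment would narrow intervals for a continuous outcome by about 5% to 20% under an assumed correlation of 0.3 to 0.6, with less to gain for binary IPH. It would be wrong to infer a biased comparison or a threat to the primary endpoint. Randomisation protects the unadjusted estimate, and the 8630 rests on deep infection alone.
- **EQ-5D-5L baseline.** This is the more important part, because it affects data the pilot is already collecting. Timing is undefined, the self-completed version on the usual route follows surgery, and sections 7.5 and 11 conflict on source. The direct numerical effect of a baseline imbalance on a 90-day QALY is small (0.0008 to 0.0021 for the assumed imbalances). The main harm is a score labelled as baseline that cannot be used as one or recovered later.

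**What to change.** 1. **Section 10.3:** add pre-induction temperature, taken before the allocated device is applied, as a covariate in the adjusted IPH/temperature models. Add the reading to the data list in section 7.5. The unadjusted analysis can stay as it is.
2. **Sections 7.5 and 11:** define the EQ-5D-5L baseline by its timing relative to randomisation and surgery, its respondent (self or proxy) and its source. Record the completion date, and reconcile the two sections.
3. **Label any score taken after surgery as post-operative** and do not use it as a pre-randomisation covariate. Adjust EQ-5D-5L and QALY models only for a score that refers to the time before randomisation, such as a pre-operative proxy or a recalled pre-fracture score. Treat a recalled score as a covariate, not automatically as the start of the QALY curve.

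The cost is one temperature field, one date field and a few sentences. If a recalled score is chosen, add a short questionnaire at an existing contact. The downside is recall or proxy error in the baseline, which reduces the precision gained.

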11. ECONOMIC EVALUATION

Good practice recommendations for cost-effectiveness analyses (Ramsey et al, 2015) suggest concentrating on the measurement of large cost drivers, with less focus on resources that are not expected to differ between different treatments. Estimation of cost-effectiveness is therefore an iterative process and, by including a health economic component, it is possible to consider how the methods might be refined in any future more definitive study.

Methods

In order to estimate costs, we will measure theatre time, length of stay and hospital re-admissions. Unit costs (e.g. Curtis et al, 2015, Dept of Health, 2014-2015) will subsequently be assigned to items of resource use. However, in order to estimate the unit costs associated with both the RAW and FAW intervention, each site will be asked to complete a short questionnaire which would request information such as the purchase price of intervention specific equipment and whether items are disposed of after each patient or re-used.

For benefits, the EQ-5D-5L (Herdman et al, 2011) will be used to measure quality of life, enabling QALY (Quality Adjusted Life Year) scores to be calculated. This will be requested at baseline, day 30 and day 90. The self-complete version of the EQ-5D-5L will be used for those who give consent, consultees will be asked to complete the proxy version of the EQ-5D-5L.

Analysis

The main purpose of the analysis is to inform the decision regarding how and what cost and effect data would be collected within the proposed fully powered trial. Thus, we will estimate completion rates and seek to identify big cost drivers, in order to inform this decision.

12. DATA MANAGEMENT

12.1. Access to Data

Direct access will be granted to authorised representatives from the Sponsor, appropriate regulatory authorities and host institution for monitoring and/or audit of the study to ensure compliance with regulations.

12.2. Data Recording and Record Keeping

Electronic CRFs will be completed by a member of the local study team using data collected from either review of routine medical records or direct contact with the participant, their consultee or their GP. Access to the electronic database management system (MACRO) will be restricted by password to authorised users and software protection applied in accordance with national data protection standards. Hard copy screening and enrolment logs will be kept within the local Trust under appropriate conditions (e.g. locked filing cabinet or locked office) such that access is restricted to the local study team and authorised personnel only. All trial data will be archived for 5 years following completion of the study.

13. QUALITY ASSURANCE PROCEDURES

The study will be conducted in accordance with the current approved protocol, International Conference on Harmonisation (ICH), Good Clinical Practice (GCP), relevant regulations and standard operating procedures. The trial sponsor will have full and free access to all aspects of the trial to allow monitoring of compliance with regulatory arrangements. A trial steering committee (TSC) will be formed that will comprise at least an independent chair person, an independent deputy chair, two independent public/patient group representatives, the Chief Investigator, Principal Investigators and the trial coordinator. The TSC will meet either in person or by teleconference at the beginning of the pilot study, after eight months of recruitment and towards the end of the pilot to (*i*) review protocol amendments and/or deviations, (*ii*) make recommendations regarding the conduct of the trial, (*iii*) review recruitment and follow-up rates, and (*iv*) assess the progression plan to a full trial based on extrapolation of data acquired in the pilot study.

A data and safety monitoring board (DSMB), comprising at least three independent and suitably qualified persons, will meet (either in person or by teleconference) to discuss the study design and SOPs shortly before the start of the study. Investigators will participate in this meeting. The DSMB will also meet prior to each TSC meeting and at any other time they deem necessary to evaluate patient safety and frequency of endpoints in an un-blinded analysis. Investigators will not be present. The DSMB may make recommendations to the TSC at any time during the pilot study and before investigators proceed with the multicentre trial.

If more than 1000 participants are recruited to the pilot study, a formal analysis of efficacy will be undertaken for presentation to the DSMB. It is expected that they would only recommend suspending the study if there was a very significantly worse outcome in one arm (e.g. using the Haybittle-Peto stopping boundary) or concerns around patient safety in relation to the trial.

Both intraoperative warming technologies are CE marked and will be used within the marketing authorisations. Therefore, the study does not fall within the remit of the Medicines for Healthcare products Regulatory Agency.

Monitoring of the study will be in accordance with a risk assessment and monitoring plan as implemented by the CTU.

